4.1 Analysis Populations

4.1.1 Safety Analysis Set

All patients who receive study drugs.

4.1.2 DLT-evaluable Analysis Set

Patients in Part 1 who receive study drug. However, this set excludes:

- Patients in Part 1 who discontinue from the study during the dose limiting toxicity (DLT) period (see Protocol Section 6.5) without experiencing a DLT

- Patients in Part 1 enrolled in the paired-biopsy cohort
- Additional patients in Part 1, of same indication, enrolled at a dose level equal or higher to the dose level for which at least 1 patient with documented PR or CR has been observed

4.1.3 Efficacy Analysis Set

All patients who receive at least 1 dose of study drug (refer to Protocol Section 6), have valid baseline disease assessment(s), and at least one valid post baseline disease assessment. Patients who do not have a post baseline assessment due to early clinical progression or death (after receiving study drug) will also be included.

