When given concomitantly, camidanlumab tesirine will be administered prior to pembrolizumab, and separated by 1 hour.

Patients, who tolerate the combination and are in disease control, would be allowed to receive additional cycles of camidanlumab tesirine in combination with pembrolizumab, starting from Cycle 5. Additional administration of camidanlumab tesirine can be given per protocol upon informing the Sponsor.

Additional administration of camidanlumab tesirine concomitantly with pembrolizumab, will be given as follow: 2 consecutive Cycles every 2 Cycles (2 Cycles on, 2 Cycles off schedule), starting from Cycle 5 for up to a year (i.e., Cycle 5 and 6, Cycle 9 and 10, Cycle 13 and 14, Cycle 17 and 18) if there is no delay in the planned treatment schedule, or, in case of delay in the administration of pembrolizumab, after respecting a minimum of 63 days (9 weeks) between the last dose of camidanlumab tesirine and the first dose of the 2 subsequent additional administrations of camidanlumab tesirine. Between these cycles, patients should receive pembrolizumab as a single agent.

Sample Size:

Approximately 95 patients; Part 1 may enroll approximately 65 patients and Part 2 will enroll approximately 30 patients.

Statistical Considerations:

Safety and tolerability analyses will be presented descriptively. ORR with 95% CI from treated patients will be presented descriptively. Duration of response, PFS, and OS will be analyzed in Kaplan-Meier approach.

SCHEDULE OF EVENTS

Table 1. Schedule of Events Every 3 Weeks (Q3W) Dosing Schedule: Camidanlumab Tesirine as Monotherapy

	Protocol Section	Screening	Treatment Period						Follow-up Period (up to 1 year from EOT)	
(1 cycle = 21 days)			Cycle 1 and Cycle 2 (C1 and C2)				C3 and beyond		EOT	Every 12 weeks (wks)
Day (D)		-21 to -1	1	3 and 5	8	15	1	8 ¹		
Informed consent	11.3	X								
Eligibility criteria	5.1 5.2	X								
Demography and Baseline Characteristics	7.2	X								
Medical/Cancer history	7.2	X								
Fresh tumor tissue collection	7.5.3.2	X prior to 1 st dose (from non-target lesion)	Optional biopsy prior to C2D1 (-1 wk window) ² and preferentially from the same site as the Baseline biopsy. This biopsy is mandatory for paired-biopsy cohorts.							
Disease assessment	7.3	X ³	6 weeks and 12 weeks after C1D1, then every 12 wks ³						X ³	Every 12 wks from EOT until disease progression ⁴
Physical examination, incl. neurological examination and check for infection	7.4.1	X	X		X	X	X		X	

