4.2.4 Follow-up Period

All patients, regardless of disease status, will be followed every 12 weeks for up to 1 year from EOT, or until withdrawal of consent, loss to follow-up, or death, whichever occurs first.

When disease assessments are not planned for a follow-up visit, the visit can be done by phone.

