9.2 Analysis Populations

- The Safety analysis set consists of all patients who receive study drug
- The DLT-evaluable analysis set consists of patients in Part 1 who receive study drug: However, this set excludes:
 - Patients in Part 1 who discontinue from the study during the DLT period (see Section 6.5) without experiencing a DLT
 - Patients in Part 1 enrolled in the paired-biopsy cohort
 - Additional patients in Part 1, of same indication, enrolled at a dose level equal or higher to the dose level for which at least 1 patient with documented PR or CR has been observed
- The Efficacy analysis set will consist of all patients who receive at least 1 dose of study drug (refer to Section 6), have valid Baseline disease assessment(s), and at least one valid post-Baseline disease assessment. Patients who do not have a post-Baseline assessment due to early clinical progression or death (after receiving study drug) will also be included.
- The PK analysis set consists of all patients who receive study drug and have at least 1 pre-(C1D1) and 1 post-dose valid assessment.

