3.3 Modifications to the statistical section of the protocol

Not applicable.

4 Statistical methods

No hypothesis testing will be performed in this study.

All analyses will use SAS® version 9.4 or higher.

Unless otherwise stated, tables, listings, and figures will be broken down by monotherapy and combination therapy and then by dose level in dose-escalation part, and by group in dose-expansion part. Additional tables broken down by indication and by indication at recommended dose for expansion (RDE) will be specified in later sections. All data will be provided in listings. Tables and figures are based on the defined analysis population.

Categorical data will be presented using counts and percentages, with the number of patients in the analysis population as the denominator for percentages. Percentages will be rounded to 1 decimal place and not be displayed for zero counts.

Continuous data will be summarized using the number of observations (n), mean, standard deviation (std), median, minimum, and maximum. Minima and maxima will be rounded to the precision of the original value, and means, medians, and 95% confidence intervals (CIs) if presented will be rounded to 1 decimal place greater than the precision of the original value. The std will be rounded to 2 decimal places greater than the precision of the original value, up to a maximum of 3 decimal places.

CI will be two-sided and use $\alpha=0.05$ (i.e., 95% CIs), unless otherwise specified. For exact estimates, the CI will be calculated using the Clopper–Pearson exact method. For Kaplan–Meier estimates, the CI will be calculated using the Greenwood's formula with (complementary) log-log transformation.

Kaplan–Meier plots will be provided along with Kaplan–Meier estimates.

The Baseline value is defined as the last non-missing value or measurement taken prior to the first dose of study drug.

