4.8 Efficacy Analyses

Efficacy analyses will be based on the Efficacy Analysis Set.

Derived efficacy endpoints and tumor assessment data will be listed.

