4.8.1 Overall Response Rate

An objective responder is defined as any patient who had a best overall response (BOR) of CR or PR per RECIST 1.1. Overall response rate (ORR) is defined as the proportion of objective responders.

For the analysis of ORR,

- The category of BOR includes complete response (CR), partial response (PR), stable disease (SD), progressive disease (PD), and inevaluable (NE).
- Overall responses derived for BOR must be assessed on or before the start of subsequent anti-cancer therapy or procedure.
- A BOR of SD requires the patient on-study for a minimum of 35 days after the first dose of study drug. A patient with SD only before this time will be considered as NE.
- For patients who do not have post-baseline assessment due to early clinical progression or death (after receiving study drug), they will be categorized separately from patients with assessments.

Disease control rate (DCR) is defined as the proportion of objective responders and patients with SD at least 35 days after the first dose of study drug.

The ORR and DCR and their 95% two-sided exact CIs will be presented. Time to first response and time to BOR will also be summarized.

BOR will also be presented by indication and by indication at RP2D. In addition, extent of study drug exposure will be summarized according to BOR category.

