4.8.5 Overall Survival

Overall survival (OS) is defined as the time from first dose of study drug until death due to any cause.

For patients who are still alive or unknown at the time of analysis, patients will be censored at the date the patient was known to be alive.

The OS will be estimated by Kaplan-Meier method. The median OS and its 95% two-sided CI will be presented.

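### The Efficacy Analysis Set makes inclusion in OS depend partly on outcome and lets ORR and DCR only equal or exceed their all-treated values; the effect is small and the remedy cheap

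*SAP*

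**What the plan says.** SAP 4.1.3 builds the Efficacy Analysis Set from patients who received at least one dose and who "have valid baseline disease assessment(s), and at least one valid post baseline disease assessment". A patient without a post-baseline assessment is kept only when the reason is early clinical progression or death. Protocol 9.2 gives the same rule, including the condition of "at least one valid post-Baseline disease assessment". Neither document defines a valid assessment.

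SAP 4.8 states: "Efficacy analyses will be based on the Efficacy Analysis Set". No endpoint is exempted. SAP 4 computes percentages "with the number of patients in the analysis population as the denominator for percentages".

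SAP 4.8.5 reads: "Overall survival (OS) is defined as the time from first dose of study drug until death due to any cause". No tumour assessment enters that definition. Protocol 4.2.4 plans follow-up to match: "All patients, regardless of disease status, will be followed every 12 weeks for up to 1 year from EOT".

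The protocol synopsis, under Statistical Considerations, says: "ORR with 95% CI from treated patients will be presented descriptively". All treated patients form the Safety Analysis Set (SAP 4.1.1), not the Efficacy Analysis Set.

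**The concern.** Take two treated patients, neither with a post-baseline scan. One dies early and is kept. The other is alive, stopped for another reason, and is left out. Both have a survival time from first dose. Membership of the OS population is thus decided partly by the outcome that OS measures.

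For ORR and DCR the issue is the denominator. A patient without a valid baseline or post-baseline assessment has no RECIST response and no stable disease at 35 days or later. Such a patient can never be in the numerator, and the rule removes the patient from the denominator as well. SAP 4.8.1 already has a not-evaluable category that could hold these patients.

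At stake is the reading of the expansion groups, planned at about 16 and 14 patients, where one patient shifts a percentage visibly.

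**Working it through.** **1. The plan's own figures.** Protocol 1.3.4 reports best response for the 44 treated monotherapy patients: 11 with stable disease, 23 with progression, 2 not evaluable and 8 with no post-baseline evaluation. 11 + 23 + 2 + 8 = 44, so all are accounted for. The percentages reproduce on a denominator of 44 (11/44 = 25.0%, 23/44 = 52.3%, 8/44 = 18.2%), except that 2/44 is 4.5% where 4.4% is printed, a rounding slip. The 8 split into deaths (5/44 = 11.4%) and clinical progressions (3/44 = 6.8%). The exception therefore keeps all 8.

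**2. Direction for ORR and DCR.** Let x be the numerator, N the number treated and k the number left out. The rate goes from x/N to x/(N − k), a change of xk/[N(N − k)]. This is never negative, and it is positive when x and k are both above zero.

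**3. Monotherapy.** The 2 not-evaluable patients are listed apart from the 8 without an evaluation. The natural reading is that they had an evaluation, so k = 0. The upper bound is k = 2. Intervals are Clopper-Pearson 95%, as SAP 4 specifies.

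| | k = 0 | k = 2 |
|---|---|---|
| ORR | 0/44 = 0% (0 to 8.0) | 0/42 = 0% (0 to 8.4) |
| DCR | 11/44 = 25.0% (13.2 to 40.3) | 11/42 = 26.2% (13.9 to 42.0) |

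The DCR change is 11 × 2/(44 × 42) = 1.2 points at most.

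**4. Expansion groups, worst-case illustration.** The documents give no loss rate for the combination. Carrying over the upper bound 2/44 is an assumption, and so are the responder counts.

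- Expected loss: 16 × 2/44 = 0.73 in Group 1 and 14 × 2/44 = 0.64 in Group 2.
- Chance of no loss: (42/44)^16 = 48% and (42/44)^14 = 52%. Chance of two or more: 16% and 13%.
- One loss in Group 1: 4/16 = 25.0% (7.3 to 52.4) becomes 4/15 = 26.7% (7.8 to 55.1).
- One loss in Group 2: 3/14 = 21.4% (4.7 to 50.8) becomes 3/13 = 23.1% (5.0 to 53.8).

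**5. OS.** Take 16 treated patients, one of them unscanned and left out. Suppose s of the other 15 are alive at some time, with follow-up complete.

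- Left-out patient still alive: all-treated survival is (s + 1)/16 and the set gives s/15, which is lower whenever s is below 15.
- Left-out patient has died: all-treated survival is s/16 and the set gives s/15, which is higher whenever s is above zero.

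For scale, the monotherapy early-death share gives 16 × 5/44 = 1.8, about 2 early deaths. With the left-out patient alive, early survival reads 13/15 = 86.7% instead of 14/16 = 87.5%. Later the sign depends on how long that patient lives.

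**6. How a treated patient can lack a post-baseline scan.** Loss to follow-up or withdrawal of consent before the first on-treatment scan is one route. The other is the waiver in Protocol 7.3: the end-of-treatment scan need not be repeated if one was done within 8 weeks (56 days), and the baseline scan may be up to 4 weeks (28 days) before Cycle 1 Day 1. Since 56 − 28 = 28, an end-of-treatment visit in the first 28 days always meets the waiver on the baseline scan alone. With a baseline scan on the day before dosing, the window runs to day 55. The first scheduled scan is at 42 ± 7 days. The patient is left out only if no later scan is obtained either.

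**The case against.** The strongest reply is that the rule is prespecified, identical in protocol body and SAP, and already counts early deaths and early clinical progressions as non-responders. That closes the main route to an inflated response rate. In the trial's own monotherapy data it covers every patient without an evaluation. No hypothesis is tested, disposition is reported on the Safety Analysis Set, and full listings let a reader recompute. All of this stands, and it is why the point is minor.

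The routes to exclusion are also narrow. Measurable disease is an entry criterion, so a treated patient without a valid baseline should be rare. After withdrawal of consent no further data are collected, so a wider population adds only a short censored survival time for that patient. This stands too.

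A reader might infer that imaging ends once a patient who stopped early starts new therapy, which would widen the gap. The documents do not say so. Protocol 7.3 and the schedule footnotes tie follow-up imaging to the reason for stopping study drug. A patient who stops for toxicity and begins new therapy later still meets that condition. Only a patient who stops in order to start other therapy falls outside it.

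A reader might also see two competing ORR definitions, because the synopsis speaks of treated patients. Every member of the Efficacy Analysis Set is treated, and the synopsis does not say all treated. This is loose wording rather than a contradiction.

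None of this answers the OS point: a scan-dependent population has no function for an endpoint that needs no scan.

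**Conclusion.** The point holds as a minor one. Inclusion in OS depends partly on outcome, and ORR and DCR in the set can only equal or exceed their all-treated values. Both follow from the definitions and need no assumption about numbers.

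The size is small and may be zero. In monotherapy ORR is unchanged, and DCR rises by 0 to at most 1.2 points within an interval about 27 points wide (40.3 − 13.2 = 27.1). One loss in an expansion group moves ORR by about 1.6 to 1.7 points under the assumed responder counts.

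Two stronger readings are not supported. A reader might take 2/44 as the expected loss rate, but it is an upper bound from a different treatment, and the natural reading of the monotherapy data is no loss. A reader might also conclude that OS will look too pessimistic. That is so only while the left-out patients are alive; over the whole curve the bias has no fixed direction.

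**What to change.** - Analyse OS, and the main ORR and DCR, in all treated patients (the Safety Analysis Set).
- Count patients without a valid post-baseline assessment as not evaluable and non-responding, and report their number and reasons by dose level and group.
- Keep the current Efficacy Analysis Set as a supportive, response-evaluable analysis, and define a valid assessment.
- As a wording note, align the synopsis sentence with Protocol 9.2 and SAP 4.1.3 and 4.8.

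The cost is a few lines in each document and one change of population flag. No new data are needed. The only downside is that reported ORR and DCR may be slightly lower.

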4.1.4 Pharmacokinetics (PK) Analysis Set

All patients who receive study drugs and have at least 1 pre-(C1D1) and 1 post-dose valid PK assessment.

4.2 Patient Disposition

Enrolled subjects include all patients who signed informed consent forms. All subjects enrolled, including screen fails, will be summarized. Subjects who discontinued treatment and discontinued from the study will be summarized, along with the primary reasons for discontinuation. The disposition summary will be based on the Safety Analysis Set.

Patient disposition data will be listed.

4.3 Protocol Deviations

All protocol deviations will be determined prior to database lock and will be agreed upon by a review of individual subject data. Major protocol deviation criteria will be established and subjects with major protocol deviations will be identified and documented before the database lock for the primary analysis.

The number and percentage of patients with any important clinical study report (CSR)-reportable protocol deviation will be summarized overall and by type of deviation. The pre-defined important CSR-reportable protocol deviations are listed below; in addition, any other protocol deviations deemed by ADCT medical to be important CSR-reportable deviations will be included in the summary.

- Patient entered the study even though they did not satisfy the entry criteria

- Patient received a prohibited concomitant treatment during the study
- Patient who met criteria for mandatory study drug discontinuation during the study but did not have study drug withdrawn
- Patient who received the wrong treatment or incorrect dose, including dose not specified in the protocol and actual dose of study drug was greater than 15% more or less than protocol planned dose.

Important protocol deviations will be summarized and listed.

4.4 Demographic and Baseline Characteristics

Demographic and baseline characteristics will be tabulated for the Safety Analysis Set.

Demographic and baseline characteristics data will also be listed.

4.5 Cancer History and Medical History

Cancer history, prior radiotherapy, prior cancer surgery, and prior system treatments will be tabulated for the Safety Analysis Set.

Cancer history, including each tumor type, medical history, prior radiotherapy, prior cancer surgery, and prior system treatments will be listed.

4.6 Prior and Concomitant Medications (other than anticancer therapies)

All medications will be recorded in the CRF starting from the ICF signature date or from 14 days prior to C1D1, whichever is earlier, and continuing until 30 days after last dose of study drug.

All medications will be coded using the World Health Organization-Drug Dictionary (WHO-DD) version 2018 March 01.

Prior and concomitant medications will be listed.

4.7 Exposure to Treatment

4.7.1 Extent of Study Drug Exposure

Study drug exposures will be based on the Safety Analysis Set.

A treatment cycle is defined as 3 weeks (i.e., 21 days).

For patients receiving camidanlumab tesirine as monotherapy, camidanlumab tesirine will be administered as an intravenous (IV) infusion on Day 1 of each cycle starting from Cycle 1 onwards.

For patients receiving camidanlumab tesirine in combination with pembrolizumab, camidanlumab tesirine will be administered for 2 cycles (on C1D1 and C2D1), and pembrolizumab at a dose of 200 mg Q3W will be administered on Day 1 of each cycle starting from Cycle 1 onwards (dosing schedule 1). If unacceptable toxicity (Protocol section 6.5) occurs during Cycle 1 at dose level -1 and dose level -2, dosing schedule 2, where pembrolizumab administration may start at Cycle 2, may be investigated in newly enrolled patients.

Patients who tolerate the study treatment (i.e., no liver enzyme increase \geq Grade 2, no pleural effusion \geq Grade 2, no edema \geq Grade 2) and are in disease control (defined as disease control \geq SD) may receive additional doses of camidanlumab tesirine in combination with pembrolizumab, upon informing the Sponsor.

Additional administrations of camidanlumab tesirine in combination with pembrolizumab will be given as follows: 2 consecutive Cycles every 2 Cycles (2 cycles on, 2 cycles off schedule), starting from Cycle 5 up to a year (i.e., Cycle 5 and 6, Cycle 9 and 10, Cycle 13 and 14, Cycle 17 and 18) if there is no delay in the planned treatment schedule: Between these cycles, patients should receive pembrolizumab as a single agent

Study treatment is given for up to a year. Continued administration of camidanlumab tesirine as monotherapy or camidanlumab in combination with pembrolizumab, or pembrolizumab alone after a year will be discussed with the Sponsor in the context of the likely risk benefit assessment for each individual patient. The dose amounts of camidanlumab tesirine monotherapy are given according to Protocol section 6.3 and for the combination with pembrolizumab according to Protocol section 6.4.

Duration of treatment (days) is calculated as date of last treatment – date of first treatment + 1.

- Camidanlumab tesirine

Dose administered at each infusion (μ g) of camidanlumab tesirine is calculated by concentrated investigational product (IP) volume (in mL) * 5 mg/mL * 1000. For cases of incomplete infusion, adjust the calculated prepared dose by multiplying a factor of (1- volume of dosing solution not administered [in mL]/ 50 mL). If volume of dosing solution not administered is missing, then adjust the calculated prepared dose by multiply the factor of (end time – start time [in minutes])/30 minutes.

Relative dose intensity (%) for camidanlumab tesirine is calculated as $100 * [\text{total weighted adjusted dose received } (\mu\text{g/kg}) / \text{total planned dose } (\mu\text{g/kg})]$, where total planned dose is number of cycles should be for camidanlumab tesirine dosing during treatment * protocol planned dose ($\mu\text{g/kg}$) per cycle.

Table 1 Target study day for camidanlumab tesirine

Study Visit	Target Study Camidanlumab Monotherapy	Day when Tesirine as	Target Study Camidanlumab in Combination with Pembrolizumab
C1D1	1		1
C2D1	22		22
C3D1	43		NA
C4D1	64		NA
C5D1	85		85
C6D1	106		106
C7D1	127		NA
C8D1	148		NA
C9D1	169		169
C10D1	190		190
C11D1	211		NA
C12D1	232		NA
C13D1	253		253
C14D1	274		274
C15D1	295		NA
C16D1	316		NA
C17D1	337		337
C18D1	358		358

Note: If patients receive doses beyond C18, target study day at each cycle will be calculated by adding 21 days from target study day in the previous cycle.

Duration of treatment, number of cycles dosed, total dose received (μ g), total weight adjusted dose received (μ g/kg), average dose per cycle (μ g/kg), dose modification, delay, reduction, and interruption, and relative dose intensity for camidanlumab tesirine will be summarized.

- Pembrolizumab

Dose administered at each infusion (mg) of pembrolizumab is fixed at 200 mg as a 30 minutes IV infusion (starting 1 hour after the end of the camidanlumab tesirine infusion), and dose modifications are not expected. For incomplete infusion, adjust the calculated prepared dose by multiplying a factor of (1- volume of dosing solution not administered [in mL]/ 50 mL). If volume of dosing solution not administered is missing, then adjust the calculated prepared dose by multiply the factor of (end time – start time [in minutes])/30 minutes.

Relative dose intensity (%) for pembrolizumab is calculated as $100 * [\text{total dose received (mg)} / \text{total planned dose (mg)}]$, where total planned dose is number of cycles should be for pembrolizumab dosing during treatment * 200 (mg) per cycle.

Duration of treatment, number of cycles dosed, total dose received (mg), average dose per cycle (mg), dose delay, reduction, and interruption, and relative dose intensity for pembrolizumab will be summarized.

Exposure data and infusion details in both camidanlumab tesirine and pembrolizumab will be listed.

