6.2.2 Preparation and Administration

6.2.2.1 Camidanlumab Tesirine

The amount of the product to be diluted will depend on the dose level and the body mass of the patient. Of note, a cap on the administered dose is to be applied for patients with a body

mass index ≥ 35 kg/m²; these patients will be dose based on a body mass index of 35 kg/m². Additional details are included in the pharmacy manual.

Administration of camidanlumab tesirine will be performed by the Investigator or a qualified designee according to the pharmacy manual.

Camidanlumab tesirine is administered as a 30-minute intravenous (IV) infusion on Day 1 of each cycle.

Variations in infusion times due to minor differences in IV bag overfill/underfill and the institution's procedure for flushing chemotherapy lines will not result in protocol deviation.

Extravasation of camidanlumab tesirine may be associated with local irritation, swelling, pain, or tissue damage. The IV infusion site should be monitored for signs of IV infiltration or drug extravasation, and patients should be instructed to report immediately any signs of IV infiltration or drug extravasation during or after the infusion. Suspected extravasation of camidanlumab tesirine should be managed according to institutional protocol for management of extravasation of cytotoxic chemotherapy.

For patients who have a central line, administration of camidanlumab tesirine via this central line should be considered.

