6.6.1.2 Guidelines for Dose Modification: Specific Non-hematologic Toxicities

Adverse Event	Grade	Camidanlumab Tesirine Management Guideline
Infusion-related reactions	1	
The infusion rate may be decreased or temporarily interrupted to permit resolution of the event. If the total time for dilution into the IV bag and infusion takes longer than 4 hours, the remaining solution of camidanlumab tesirine will be discarded and the dosing will continue with the assigned dose at the next scheduled dosing visit.
 
Please refer to Section 6.9.4 for treatment recommendation.

Adverse Event	Grade	Camidanlumab Tesirine Management Guideline
	2	
Interrupt camidanlumab tesirine infusion to permit resolution of the event. If the event resolves within the total time of 4 hours after dilution into the IV bag and infusion time, resume camidanlumab tesirine infusion at 50% of the prior infusion rate, still not exceeding the total of 4 hours after infusion has restarted.
 
If the resolution takes longer than the total 4 hours, the remaining solution of camidanlumab tesirine will be discarded, and the dosing will continue with the assigned dose at the next scheduled dosing visit at 50% of the prior infusion rate.
 
Please refer to Section 6.9.4 for treatment recommendation.

	3	
Permanently discontinue camidanlumab tesirine.
 
However, if the AE resolves within 24 hours after onset (with or without clinical management), dosing may continue with the assigned dose at the next scheduled dosing visit at 50% of the prior infusion rate.
 
Please refer to Section 6.9.4 for treatment recommendation.

	4	Permanently discontinue camidanlumab tesirine.

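### The SAP's clock-time fallback for incomplete infusions has no cap and ignores pauses and rate changes, so it can overstate the dose delivered

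*SAP*

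**What the plan says.** SAP 4.7.1 derives the dose given at each infusion. The adjustment is confined to infusions that were not completed: "For cases of incomplete infusion, adjust the calculated prepared dose by multiplying a factor of" one minus the undelivered volume over 50 mL. A second rule covers records without that volume: "If volume of dosing solution not administered is missing, then adjust the calculated prepared dose by multiply the factor of". What follows is a ratio of clock time to nominal duration, given as "end time – start time [in minutes])/30 minutes". The same pair of rules is written for camidanlumab tesirine and for pembrolizumab. The SAP sets no upper limit on the time factor, makes no deduction for pauses, gives no weight to infusion rate, and does not say which moment counts as the end time when an infusion is interrupted. The result feeds total dose, average dose per cycle and relative dose intensity.

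Protocol 6.2.2.1 supplies the denominator: "Camidanlumab tesirine is administered as a 30-minute intravenous (IV) infusion on Day 1 of each cycle". Protocol 6.6.1.2 then describes infusions that do not run that way. For a Grade 1 infusion reaction, "The infusion rate may be decreased or temporarily interrupted to permit resolution of the event". For Grade 2 the infusion is stopped until the event resolves, and sites then "resume camidanlumab tesirine infusion at 50% of the prior infusion rate". Some later doses after Grade 2 or Grade 3 reactions also run at half the prior rate. The remainder is thrown away under a time limit, worded for Grade 1 as "If the total time for dilution into the IV bag and infusion takes longer than 4 hours".

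**The concern.** Elapsed time over 30 minutes measures the delivered fraction only if drug flows at the nominal rate from the recorded start to the recorded end. The protocol's handling of infusion reactions breaks that condition: a pause adds minutes with no flow, and half rate adds minutes that each deliver half as much. An incomplete infusion cannot have delivered more than the prepared dose, yet the factor can say that it did.

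At stake is the direction of the exposure summary. A patient whose infusion was cut short could appear with above-plan relative dose intensity, in a study whose primary objective is safety and tolerability. Exposure is tabulated by dose level, and 3+3 cohorts are small, so a single record can move a cohort mean.

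**Working it through.** The plan gives no worked figure for this derivation, so there is none to reproduce. The check is direct arithmetic.

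**Inputs from the documents.** Nominal duration 30 minutes (Protocol 6.2.2.1; SAP 4.7.1). Resumption at 50% of the prior rate (Protocol 6.6.1.2).

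**Assumptions.** Prepared dose equals planned dose, and the prior rate is the nominal one. All segment times are illustrations; the documents report none.

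**Formulas.** Let t1 be minutes at full rate, P minutes paused and t2 minutes at half rate.
- Delivered fraction d = (t1 + 0.5 × t2)/30
- SAP factor f = (t1 + P + t2)/30
- Overstatement f − d = (P + 0.5 × t2)/30

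The overstatement is zero only when P and t2 are both zero. The factor exceeds 1 when t1 + P + t2 is more than 30, whereas d is below 1 for any incomplete infusion.

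| Assumed course | Elapsed (min) | Delivered d | SAP factor f |
|---|---|---|---|
| Full rate, stopped for good at 15 min | 15 | 15/30 = 0.50 | 15/30 = 0.50 |
| 10 full + 60 pause + 20 half rate | 90 | (10 + 10)/30 = 0.667 | 90/30 = 3.00 |
| 15 full + 30 pause + 10 half rate | 55 | (15 + 5)/30 = 0.667 | 55/30 = 1.833 |
| Half rate throughout, stopped at 40 min | 40 | 20/30 = 0.667 | 40/30 = 1.333 |
| Half rate throughout, stopped at 20 min | 20 | 10/30 = 0.333 | 20/30 = 0.667 |
| 5 full + 10 pause + 10 half rate | 25 | (5 + 5)/30 = 0.333 | 25/30 = 0.833 |

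The first row is the case the rule fits. The last two rows overstate the dose while staying below 1, so they would not look odd in a listing.

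**End time.** Take 10 minutes at full rate, never resumed. If end time is last flow, f = 10/30 = 0.333, which is correct. If end time were entered at discard, say at 240 minutes, f = 240/30 = 8.00. The SAP does not settle which applies.

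**Effect on relative dose intensity.** Take two planned camidanlumab tesirine cycles, one complete and one following the 15 + 30 + 10 course. True value: (1 + 0.667)/2 = 83.3%. SAP value: (1 + 1.833)/2 = 141.7%. In a cohort of three with the other two patients at 100%, the mean is (100 + 100 + 141.7)/3 = 113.9% instead of (100 + 100 + 83.3)/3 = 94.4%.

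**Would a cap alone do?** No. Capped at 1, the 10 + 60 + 20 course scores 100% against 67%, and half rate stopped at 20 minutes still scores 67% against 33%.

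**The case against.** The rule is narrow. It needs an infusion that was both incomplete and lacking an undelivered volume; a slowed or paused infusion that is completed is not adjusted at all. The illustrated courses also need something beyond the prescribed sequence. In the 10 + 60 + 20 example another 20 minutes at half rate would complete the dose, at 110 minutes in total, so stopping at 90 requires a further cause or a long dilution time. All of this stands and limits the reach of the point. Nor do the documents say why infusions are left incomplete. Infusion reactions are one route, but Protocol 6.2.2.1 also discusses extravasation.

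Exposure summaries are descriptive, no hypothesis is tested, and neither the DLT definition nor the escalation rule uses this factor. SAP 6.1.1 has suspect data queried and SAP 4.7.1 lists infusion details, so a value of 300% would probably be noticed. That is fair, but a query does not change the formula, and overstated values below 100% would pass.

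A reader might infer that partial doses will be recorded as overdoses, or will create false protocol deviations. The documents do not support this. Protocol 6.7 defines overdose by the dose given, with prompt reporting by the site, and nothing ties it to the SAP derivation. SAP 4.3 lists as a deviation that the "actual dose of study drug was greater than 15% more or less than protocol planned dose", but does not say that the derived dose is used, and deviations are agreed by reviewing individual patients' data. In the 67% examples the true dose is already more than 15% below plan, so a flag would be right in any case. A nearly complete infusion would differ (half rate stopped at 59 minutes: 98.3% delivered, factor 1.967), but only if the derived dose drove the test, which is not stated.

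A reader might also extend the conflict to pembrolizumab. The formula is repeated for that drug, but the pause and half-rate rules in Protocol 6.6.1.2 are for camidanlumab tesirine. Protocol 6.2.2.2 refers to prescribing information for pembrolizumab infusion reactions.

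**Conclusion.** The fallback is wrong as written for an incomplete camidanlumab tesirine infusion that was paused or slowed and has no undelivered volume recorded. The size of the error depends entirely on the assumed times: 133% to 300% against 67% delivered in three of the illustrations, and 67% or 83% against 33% in the two that stay below 100%. For pembrolizumab the same formula has the same weakness, without a protocol rule shown to trigger it. The documents give no count of affected records; few are likely. Severity is minor. The point concerns the exposure derivation only, and makes no claim about overdose reporting, deviation counts or how infusions should be managed.

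**What to change.** Amend the fallback in SAP 4.7.1 for both drugs:

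- Define end time as the moment of last flow, and cap the factor at 1.
- Where pause and rate data are recorded, use factor = running minutes, excluding pauses and weighted by the fraction of nominal rate, divided by 30.
- Where the infusion was paused or slowed and those data are not recorded, set that infusion's delivered dose to missing and flag it. Show relative dose intensity over the range from 0% to 100% for that infusion. In the two-cycle example the range is (1 + 0)/2 = 50% to (1 + 1)/2 = 100%, which contains the true 83.3%.

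Treating the dose as missing agrees with the SAP 6.1.1 default of no imputation. The cost is a few lines of SAP text and a check of what the CRF collects, since neither document shows that pause times and rates are captured. The downside is that a few infusions may have a missing dose, possibly in patients who tolerated the drug poorly. The range is there to keep them visible.
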